4.6 PATIENT WITHDRAWAL AND DISCONTINUATION

Patients have the right to withdraw from the study at any time without needing to give any reason. Should a patient withdraw, all efforts should be made to complete and report observations prior to withdrawal as thoroughly as possible. Patients who choose to discontinue from the study will not be replaced.

The Investigator may withdraw patients in the event of intercurrent illness, AEs, protocol violations, administrative or other reasons. The Investigator is strongly encouraged to contact the Medical Monitor prior to discontinuation of study drug or withdrawal of patient from the study.

Discontinuation of PEX or discontinuation from the study is **mandatory** for:

- Patients whose baseline VO₂MAX is more than ±20% of their screening VO₂MAX, *i.e.*;
(*BASELINE VO₂MAX* – *SCREEN VO₂MAX*)/ *SCREEN VO₂MAX* > ±20%
- Patients who are unable or unwilling to return to the study site to repeat a CPEX test that did not meet the prospectively defined acceptance criteria as determined by the centralized CPEX assessor
- Patients identified as PMs of PEX at the week 1 (day 8) study visit. Despite the screening genotyping, which is 95-97% effective at identifying PMs, there may be a limited number of phenotypic PMs. Phenotypic PM subjects will be identified by determination of the PEX metabolic ratio (MR). This MR is the ratio of CIS to the parent compound, PEX. If the CIS:PEX is <0.4, the patient will be deemed a phenotypic PM regardless of genotype. These patients are at risk for clinically significant elevated plasma PEX levels. Such elevated plasma levels could decrease tolerability or increase the risk of short, self-limited toxicity; if unchecked longer term toxicities could result. Hence, as with the genotypic PMs, these phenotypic PM subjects will be withdrawn from the study. (Patients with a CIS:PEX ratio <0.4 after the week 1 visit will not automatically be withdrawn from the study. These patients should be further evaluated and the patient status will be discussed with the Medical Monitor.)
- Patients with persistent elevations in ALT or AST; see Appendix C for the definition of “persistent”
- Female study participants discovered to be pregnant during the treatment period

Discontinuation of PEX should be considered in the following situations [Phan *et al.*, 2009a] following discussion with the Medical Monitor:

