- R. Study-drug will be dispensed once the ECG Corelab confirms that the Baseline ECG meets the entry criteria. The first study-drug dose will be administered under the supervision of the study-site staff once the study-site staff confirm that the Baseline VO₂MAX is within $\pm 20\%$ of the Screening CPEX.

Note:

- If for any reason the ECG Corelab is not able to immediately confirm the ECG outcome, the patient will return home without receiving any dispensed study-drug. In such cases, once the ECG Corelab confirmation becomes available the patient will return to the site to collect the study-drug supply. The patient will then commence study-drug dosing (defined as Day 1).
 - All Baseline ECG confirmations will be received by study sites from the ECG Corelab within a maximum of 48h.
 - Before dosing has commenced; if the centralized CPEX assessor confirms the Baseline VO₂MAX is not within $\pm 20\%$ of the Screening CPEX then the patient will not enter the study
 - Before dosing has commenced; if the centralized CPEX assessor confirms an invalid Baseline VO₂MAX the patient will be invited to repeat the Baseline CPEX test within the 28-day period allowed between Screening and the start of study-drug dosing
 - After dosing has commenced; if the centralized CPEX assessor deems the Baseline CPEX test to have been invalid or not within $\pm 20\%$ of the Screening CPEX then the patient will remain in the study and the patient's Screening CPEX result will be taken as the valid Baseline result
 - All Baseline CPEX confirmations will be received by study sites from the centralized CPEX assessor within a maximum of 48h.
- S. AEs should be documented and recorded at each visit. All AEs (serious and non-serious, and related and non-related) will be documented and recorded through the Follow-Up visit. Patients must be followed for AEs until the final required protocol visit or until all drug-related toxicities and SAEs have resolved (or are considered chronic/stable).
- T. If an AE is determined to have been the result of a PEX-CIS Assay abnormality (e.g., false positive, false negative, measurement error), it will be deemed an ADE for the purpose of device reporting.
- U. Concomitant Medications should be collected and recorded at each visit. All concomitant medications received up to and including 30 days prior to the start of study medication through the Follow-Up visit will be recorded.

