6.4 PERIOD 1: BASELINE VISIT AND COMMENCEMENT OF STUDY-DRUG DOSING

Once a patient has met the entry criteria for the study and completed all of the screening procedures they will then visit the study site for the baseline visit and commencement of study-drug dosing in Period 1. At this visit the following will be completed:

- A 12-lead ECG will be recorded in triplicate
 - ECGs should be taken prior to CPEX testing or blood draws and obtained after the patient has been resting comfortably in a supine position for approximately 10 minutes

- The baseline ECG must not meet any of the exclusion criteria detailed in section 4.3.2; this must be confirmed by the central ECG reader before study-drug can be dispensed to the patient
- CPEX testing will follow ECG recording
 - The Baseline VO₂MAX must not exceed $\pm 20\%$ of the Screening VO₂MAX with the screening test being the reference (i.e., $(BASELINE\ VO_2MAX - SCREEN\ VO_2MAX) / SCREEN\ VO_2MAX \leq \pm 20\%$); this will be calculated by study-site staff in order to allow a decision on patient inclusion in the study during the Baseline site-visit
 - All Baseline CPEX test validation reports will be received by study sites from the centralized CPEX assessor within a maximum of 48h; the timing of the availability of the centralized CPEX assessor report will define the following status for the patients:
 - CPEX Report BEFORE study-drug dosing has started shows VO₂MAX is not within $\pm 20\%$ of the Screening CPEX; the patient will not enter the study
 - CPEX Report BEFORE study-drug dosing has started shows an invalid test; the patient will be invited to repeat the Baseline CPEX test within the 28-day period allowed between Screening and the start of study-drug dosing
 - CPEX Report AFTER study-drug dosing has started shows an invalid test or shows VO₂MAX is not within $\pm 20\%$ of the Screening CPEX; the patient will remain in the study and the patient's Screening CPEX result will be taken as the valid Baseline result
- Vital signs and body weight, will be measured; heart rate and blood pressure will be measured in the seated position after 5 minutes of rest
- Urine sampling for an on-site urine pregnancy test for female patients of child bearing potential
- Study-drug storage, dosing and accountability instructions will be reviewed with the patient
- Study-drug sufficient for daily dosing until the next scheduled patient visit to the study site will be dispensed to the patient

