- i. If for any reason the ECG Corelab was not able to immediately confirm the ECG outcome, the patient was to return home without receiving any dispensed study-drug. In such cases, once the ECG Corelab confirmation became available the patient was to return to the site to collect the study drug supply. The patient was then to commence study-drug dosing (defined as Day 1).
 - ii. All Baseline ECG confirmations were to be received by study sites from the ECG Corelab within a maximum of 48h.
 - iii. Before dosing commenced; if the centralized CPEX assessor confirmed the Baseline VO_{2MAX} was not within $\pm 20\%$ of the Screening CPEX then the patient was not to enter the study
 - iv. Before dosing commenced; if the centralized CPEX assessor confirms an invalid Baseline VO_{2MAX} the patient was to be invited to repeat the Baseline CPEX test within the 28-day period allowed between Screening and the start of study-drug dosing
 - v. After dosing commenced; if the centralized CPEX assessor deems the Baseline CPEX test to have been invalid or not within $\pm 20\%$ of the Screening CPEX then the patient was to remain in the study and the patient's Baseline CPEX result will be taken as the valid Baseline result
 - vi. All Baseline CPEX confirmations were to be received by study sites from the centralized CPEX assessor within a maximum of 48h.
- S. AEs were to be documented and recorded at each visit. All AEs (serious and non-serious, and related and non-related) were to be documented and recorded through the Follow-Up visit. Patients were to be followed for AEs until the final required protocol visit or until all drug-related toxicities and SAEs have resolved (or are considered chronic/stable).
- T. If an AE was determined to have been the result of a PEX-CIS Assay abnormality (e.g., false positive, false negative, measurement error), it will be deemed an ADE for the purpose of device reporting.
- U. Concomitant Medications was to be collected and recorded at each visit. All concomitant medications received up to and including 30 days prior to the start of study medication through the Follow-Up visit were to be recorded

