3 ANALYSIS VARIABLES

3.1 Efficacy Variables

3.1.1 Primary efficacy variable

The primary endpoint of the study is the change from Baseline of VO₂MAX at the end of Period 2. Cardio-Pulmonary Exercise Testing (CPEX) was to be performed at Screening and repeated at Baseline (Day 1), at the end of Period 1 (Week 8) and the end of Period 2 (Week 16). Details of the exercise test performed and the resultant VO₂MAX evaluations were to be reported in the CRF. For entry into the study, the patient's VO₂MAX at Screening could not exceed 75% of the predicted age-adjusted value and the VO₂MAX at Baseline (Day 1) could not be outside $\pm 20\%$ of the Screening VO₂MAX value (if the centralized CPEX assessor deems the Baseline CPEX test is not within $\pm 20\%$ of the Screening CPEX after dosing with study medication has already commenced, the subject will remain in the study and the subject's Baseline CPEX result will be taken as the valid Baseline result, unless it is deemed invalid or if the CPEX test was administered after the start of study medication).

CPEX reports were to be validated by a centralized CPEX assessor.

The VO₂MAX at the Day 1 assessment will be regarded as Baseline unless the CPEX was reported to have been assessed after the start of study medication. If this situation arises, the VO₂MAX from Screening will be regarded as Baseline. Changes and percent changes from Baseline to the end of Period 2 VO₂MAX value will be derived:

$$\text{Change at Period 2} = \text{Period 2 VO}_{2\text{MAX}} - \text{Baseline VO}_{2\text{MAX}}$$

$$\text{Percent Change at Period 2} = (\text{Period 2 VO}_{2\text{MAX}} - \text{Baseline VO}_{2\text{MAX}}) / \text{Baseline VO}_{2\text{MAX}}$$

If the patient withdraws from the study early, but provides an unscheduled or early end-of-Period 2 VO₂MAX assessment then this VO₂MAX assessment will be used in the derivation of efficacy endpoints. Only if the unscheduled or early end-of-Period 2 VO₂MAX assessment is within ± 7 days of the intended target assessment (Period 2 target = Day 113), relative to Day 1, will the derived change in VO₂MAX be used in the primary analysis using the Completer Population (see section 7.1, below).

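### When the central CPEX report arrives after the first dose, Protocol and SAP give conflicting Baseline VO₂MAX rules, and SAP section 12 does not list the departure

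*Protocol*

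**What the plan says.** **How the case arises.** Under Protocol 6.4 the site compares Day 1 VO₂MAX with Screening itself: "this will be calculated by study-site staff in order to allow a decision on patient inclusion in the study during the Baseline site-visit". Once the ECG is cleared, the first dose can be given at that visit. The central CPEX report may take up to 48 hours, so it can arrive after dosing has begun.

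**Protocol, report after dosing.** Section 6.4 covers both an invalid test and one outside ±20%: "the patient will remain in the study and the patient's Screening CPEX result will be taken as the valid Baseline result". Table 6.2, footnote R, gives the same rule.

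**SAP, report after dosing.** Footnote R(v) to the schedule in SAP 2.2 covers the same two situations but names the other test: "then the patient was to remain in the study and the patient's Baseline CPEX result will be taken as the valid Baseline result". SAP 3.1.1 deals with the discordant test in a parenthesis: "Baseline CPEX result will be taken as the valid Baseline result, unless it is deemed invalid", with a further exception for a test done after the start of drug. A later paragraph of 3.1.1 says that the Day 1 value "will be regarded as Baseline unless the CPEX was reported to have been assessed after the start of study medication", and then: "If this situation arises, the VO₂MAX from Screening will be regarded as Baseline".

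**SAP 12** lists three changes from the protocol: the MITT population, the use of early-withdrawal assessments, and the move from t-test to ANCOVA.

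**Protocol 4.6** puts this first in its list of mandatory reasons for discontinuation: "Patients whose baseline VO₂MAX is more than ±20% of their screening VO₂MAX". It does not distinguish patients already dosed, and it does not refer to 6.4.

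**The concern.** Baseline VO₂MAX is subtracted to form the primary change score, divides the percent change, and is a covariate in the primary ANCOVA (SAP 7.1). It also enters the Period 1 analysis (SAP 7.2.2), the snapshot t-test (SAP 10) and, as a covariate, the 6MWT models (SAP 7.2.3 to 7.2.5). Its definition should be the same everywhere and fixed before the data are seen. That matters more here than usual, because the trial is open-label and single-arm: Baseline is the only comparator.

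For a valid but discordant Day 1 test, an analyst who follows the SAP uses a value that the protocol rejects, with no recorded reason. For an invalid Day 1 test, an analyst who follows R(v) subtracts a measurement that the central assessor has ruled unusable.

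**Working it through.** **1. The rules side by side (report received after the first dose)**

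| Place | Valid Day 1 test, more than 20% off | Invalid Day 1 test |
|---|---|---|
| Protocol 6.4; Table 6.2 footnote R | Stays; Screening is Baseline | Stays; Screening is Baseline |
| SAP footnote R(v) | Stays; Day 1 is Baseline | Stays; Day 1 is Baseline |
| SAP 3.1.1, parenthesis | Stays; Day 1 is Baseline | Day 1 not accepted; no replacement named |
| SAP 3.1.1, later paragraph | Day 1 | Day 1 (only a test after the first dose goes to Screening) |
| Protocol 4.6, first bullet | Discontinue | Not covered |
| SAP 12 | Not listed | Not listed |

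In the first column, Protocol and SAP disagree on Baseline. In the second, R(v) disagrees with the protocol, and the two parts of SAP 3.1.1 disagree with each other. The footnotes differ by one word. Protocol: "then the patient will remain in the study and the patient's Screening CPEX result will be taken as the valid Baseline result". SAP: "then the patient was to remain in the study and the patient's Baseline CPEX result will be taken as the valid Baseline result".

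**2. The plan's own power figures**

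Inputs from Protocol 8.2 and SAP 11: n = 30, SD 2.5, two-sided alpha 0.05, one-sample t-test. The noncentrality is mean × √n / SD.

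- Mean 2.0: 2.0 × 5.477 / 2.5 = 4.38, power 98.9% (stated: above 95%).
- Mean 1.2: 1.2 × 5.477 / 2.5 = 2.63, power 71.95% (stated: 72%).

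Both are reproduced.

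**3. Size for one valid discordant patient**

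The documents give no Screening VO₂MAX, so 14, 18 and 22 mL/kg/min are assumed. Switching Baseline moves the change score by |Screening − Day 1|, which exceeds 0.20 × Screening. The figures below are therefore minimum shifts. The planned standard error is 2.5 / √30 = 0.456.

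| Screening (assumed) | Shift in change score | Relative to planned 2.0 | Shift in mean of 30 | Relative to SE 0.456 |
|---|---|---|---|---|
| 14 | 0.20 × 14 = 2.8 | 1.4 | 2.8 / 30 = 0.093 | 20% |
| 18 | 0.20 × 18 = 3.6 | 1.8 | 3.6 / 30 = 0.120 | 26% |
| 22 | 0.20 × 22 = 4.4 | 2.2 | 4.4 / 30 = 0.147 | 32% |

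The ANCOVA mean shifts by the same amount: a least-squares fit with an intercept, evaluated at the covariate means, returns the raw mean of the outcome. Shifts in opposite directions cancel.

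**4. Which rule gives the odd value**

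Take Screening 18 and a true gain of 2.0.

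- Day 1 is the true level. Day 1 21.6, Period 2 23.6: the protocol gives 23.6 − 18 = +5.6, the SAP gives 23.6 − 21.6 = +2.0. Day 1 14.4, Period 2 16.4: the protocol gives −1.6, the SAP +2.0.
- Screening is the true level and Period 2 is 20: the protocol gives 20 − 18 = +2.0. The SAP gives 20 − 21.6 = −1.6 or 20 − 14.4 = +5.6.

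The example is symmetric, so neither rule is shown to be the biased one.

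**5. Primary power**

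- If patients were lost under 4.6 (they are not replaced, Protocol 8.5): 98.9% at n = 30, 98.6% at 29, 97.9% at 27.
- If one of 30 has the Baseline switched (Screening 18, 200,000 simulated trials, Day 1 taken as the value that yields the planned mean): 98.9% becomes 99.3% or 97.4%, depending on direction.

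**The case against.** The best defence is that, for a valid discordant test, the SAP is clear and prospective. It gives the same rule in two places, either Baseline is defensible, and the protocol's rule sits among visit procedures, not in its statistical section. For an invalid test, Screening is the only other CPEX scheduled before dosing, and Protocol 6.4 names it, so a sensible analyst would find the answer. The case is also rare: the central reading must overturn the site's calculation and arrive after dosing.

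Most of this stands, and it limits the weight of the point. It does not remove it. A departure in deriving the primary endpoint belongs in SAP 12 wherever the protocol states the rule, and R(v) followed literally uses an invalid value.

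Four stronger readings are not supported.

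- *Dosed patients will be withdrawn under 4.6.* The 4.6 bullet and 6.4 do conflict as written, but 6.4 addresses this exact case, footnote R repeats it, and the SAP also keeps the patient. The more specific rule probably prevails.
- *The SAP's value, or the protocol's, is the distorted one.* That depends on which test reflects the patient's true level, which the documents cannot tell us.
- *The Period 1 result is at risk because its power is only 72%.* That figure matches a mean change of 1.2, but Protocol 8.2 and SAP 11 attach it to the first secondary outcome. SAP 7.2.1 defines that outcome as the Period 2 versus Period 1 comparison, and in the raw difference Baseline cancels: (P2 − B) − (P1 − B) = P2 − P1. The Period 1 snapshot test has no decision rule.
- *The change was knowingly left out.* The SAP cites protocol version 11 of 02 December 2016, and the version of the supplied protocol is not visible. A version difference or a drafting slip is possible. Either would explain the mismatch, but it would still need to be reconciled.

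**Conclusion.** The point holds as a conflict between written rules for the Baseline of the primary endpoint. A valid discordant Day 1 test has one Baseline in the protocol and another in the SAP, unlisted in SAP 12. An invalid Day 1 test is replaced by Screening in the protocol, kept by SAP R(v) and by the later paragraph of SAP 3.1.1, and rejected by the parenthesis in that same section. The gap between Protocol 4.6 and 6.4 is secondary.

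Few patients, possibly none, will be affected. For one valid discordant patient, the change score moves by at least 2.8 to 4.4 mL/kg/min and the mean of 30 by about 0.09 to 0.15, in either direction, on the assumed Screening range of 14 to 22. For an invalid test the size cannot be bounded from the documents. Primary power hardly changes, and the point does not rest on any loss of power. Severity: minor to should-fix.

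**What to change.** Before database lock, which SAP 1 sets as the limit for revisions:

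1. In SAP 3.1.1 and footnote R(v), state that a Day 1 CPEX that is invalid, or was done after the first dose, is replaced by the Screening value.
2. For a valid Day 1 test found discordant after dosing, choose one rule. Either follow the protocol and use Screening, or keep Day 1 and enter it in SAP 12 as a change with its reason. One argument for Day 1 is that patients were selected for low VO₂MAX on the Screening test. The argument for Screening is that the protocol specifies it.
3. If any such patient exists, rerun the primary analysis with the other value as a sensitivity analysis.
4. If enrolment is still open, limit the 4.6 bullet to patients not yet dosed and cross-refer to 6.4 at the next amendment.

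The cost is a few sentences in the SAP and at most one extra analysis run. Item 4 is one sentence, but it needs IRB/IEC approval under Protocol 10.2, so it should travel with another amendment. The SAP describes much of the study in the past tense, so item 4 may no longer apply.

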 - i. All CPEX test results will be reviewed by the centralized CPEX assessor for compliance with prospectively defined CPEX test acceptance criteria
 - ii. The Screening CPEX will be performed to show that patient is able to perform exercise testing but unable to exceed 75% of the predicted age-adjusted maximum level (as determined by VO₂MAX).
- G.**
 - i. A valid Screening CPEX must be confirmed by the centralized CPEX assessor before the Baseline CPEX is done
 - ii. The Baseline VO₂MAX must not vary from the screening VO₂MAX by more than $\pm 20\%$ (with the screening test being the reference); this will be calculated by study-site staff in order to allow a decision on patient inclusion in the study during the Baseline site-visit
- H.** If the centralized CPEX assessor deems the EOT CPEX test to be invalid, the subject may be required to return for a repeat test.
- I.** Heart rate and blood pressure assessed in the seated position after 5 minutes of rest.
- J.** Samples for laboratory assays will be sent to the central lab for analysis (with the exception of the urine pregnancy test at Baseline which will be performed locally).
- K.** Females of child bearing potential. (Eligible patients will be advised to use an adequate contraceptive method.)
- L.** Serum Chemistry: sodium, potassium, bicarbonate, chloride, calcium, phosphorus, glucose, creatinine, BUN, CPK, uric acid, albumin, total protein, total bilirubin, alkaline phosphatase, ALT (SGPT), AST (SGOT), LDH, total cholesterol
- M.** CBC: hemoglobin, hematocrit, RBC, MCV, MCH, MCHC, RDW, WBC count with differential (neutrophils, bands, lymphocytes, monocytes, eosinophils, basophils), platelets.
- N.** Coagulation tests: prothrombin time (PT), partial thromboplastin time (PTT), and international normalized ratio (INR).
- O.** CYP2D6 Poor Metabolizer status is defined by the CPIC guidelines.
- P.** All determinations of systemic blood levels of PEX, CIS, and TRANS will be measured using the PEX-CIS assay. Blood sampling for determination of PEX, CIS and TRANS will be scheduled approximately 12h after dosing on the previous study day. Results for PEX and CIS will be reported to the study sites for confirmation of a patient's phenotypic status for PEX metabolism and for dose-adjustment decisions.
- Q.** Patients will be provided with up to 4 weeks' worth of study medication at the Baseline, Week 2, 4, 6, 8, 10, 12 and 14 study visits.

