6.7 PERIOD 1; ADDITIONAL PROCEDURES AT COMPLETION OF WEEK 8 (DAY 57) VISIT

In addition to the procedures described above in section 6.6, the following procedures will be completed during the Period 1, Week 8 (Day 57) study visit:

- CPEX testing will be done following completion of the ECG recordings
- Body weight will be measured
- Blood samples will be obtained for routine serum chemistry safety tests and for biomarker levels of hemoglobin A1c
- The 6MWT will be done as the last procedure of the Week 8 visit

6.8 PERIOD 2: END OF TREATMENT AND AFTER COMPLETION OF WEEK 16 (DAY 113 ±3 DAYS)

Dosing should continue through the day prior to this visit. At this visit the following will be completed:

- A 12-lead ECG will be recorded in triplicate; ECGs should be taken prior to CPEX testing or blood draws and obtained after the patient has been resting comfortably in a supine position for approximately 10 minutes
- CPEX testing will be done following completion of the ECG recordings
 - If the centralized CPEX assessor deems the EOT CPEX test to be invalid, the subject may be required to return for a repeat test
- Vital signs and body weight, will be measured; heart rate and blood pressure will be measured in the seated position after 5 minutes of rest
- A blood sample will be obtained for analysis of PEX, CIS and TRANS approximately 12h after dosing on the previous study day
- Blood samples will be obtained for a complete blood cell count, routine serum chemistry safety tests and for biomarker levels of hemoglobin A1c
- Study-drug accountability will be reviewed with the patient. All remaining study-drug will be collected.
- AEs since the patient's previous site visit will be recorded. (As part of the investigation and reporting of all SAEs, every attempt will be made to obtain a blood sample for analysis of PEX, CIS and TRANS as soon as possible after awareness of an SAE.)
- ADEs will be assessed for and recorded
- Concomitant medication used since the patient's previous visit will be recorded
- A 6MWT will be done as the last procedure of the week 16 visit

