8 STATISTICAL CONSIDERATIONS

8.1 PRIMARY AND SECONDARY ENDPOINTS

8.1.1 Primary Endpoint

The primary endpoint of the study is the change from baseline of VO₂MAX at the end of Period 2 of the study.

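### A rejected Week 8 CPEX that is not repeated can cost a patient the Week 16 primary analysis, through Protocol 4.6 and separately through the Completer definition

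*Protocol*

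**What the plan says.** **The discontinuation rule.** Protocol 4.6 opens a list with "Discontinuation of PEX or discontinuation from the study is" mandatory. Its second bullet covers patients "unable or unwilling to return to the study site to repeat a CPEX test that did not meet the prospectively defined acceptance criteria". No visit is given.

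**Which tests are judged.** Footnote F to the schedule in Protocol 6.2 says: "All CPEX test results will be reviewed by the centralized CPEX assessor for compliance with prospectively defined CPEX test acceptance criteria". Week 8 is therefore included.

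**Rules by visit.**
- Baseline, before dosing: an invalid test may be repeated within the screening window (6.4, footnote R).
- Baseline, where the "CPEX Report AFTER study-drug dosing has started shows an invalid test": the patient stays in and the Screening value is used (6.4).
- Week 8: section 6.7 schedules the test ("CPEX testing will be done following completion of the ECG recordings") and says nothing about an invalid one.
- Week 16: "If the centralized CPEX assessor deems the EOT CPEX test to be invalid, the subject may be required to return for a repeat test" (6.8; footnote H has the same rule).

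**Endpoint and population.** Protocol 8.1.1 states: "The primary endpoint of the study is the change from baseline of VO₂MAX at the end of Period 2 of the study". The primary population is the Completer Population. Protocol 8.3 requires all procedures at Baseline, end of Period 1 and end of Period 2. SAP 4.1.3 adds that the Period 2 CPEX must fall within 7 days of Day 113. SAP 7.1 names this population, then says that it includes an endpoint from all patients assessed within 7 days of plan. Protocol 8.5 rules out replacement.

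**The concern.** The Week 8 value is not a term in the primary endpoint. Two separate rules nevertheless let a Week 8 test-quality problem remove a patient from the primary analysis.

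Under 4.6 the patient stops PEX or leaves, so no on-treatment Week 16 value comes into being. Under the Completer definition the patient may finish all 16 weeks with a valid Week 16 test and still be left out.

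In a single-arm trial no control group would share the loss and so reveal it. If patients who cannot or will not repeat an exercise test tend to respond less, the completer mean is too high, and part of that excess comes from the plan's own rules.

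**Working it through.** **1. Does the 4.6 bullet reach Week 8?** It needs a rejected test and a patient who cannot or will not return. All tests are judged. Baseline and end of treatment have their own text and Week 8 has none, so the general bullet is the only rule that applies there.

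**2. Could Week 16 survive on the PEX-only branch?** Section 6.8 assumes continued treatment: "Dosing should continue through the day prior to this visit". The protocol has no visit schedule for a patient who is off drug but on study. Section 6.11 attempts a CPEX only in patients who choose to withdraw. A test near Day 57 is 113 − 57 = 56 days from target, far outside the ±7 days of SAP 3.1.1 and 5.3, so it could serve only the supportive MITT analysis.

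**3. Would changing 4.6 alone be enough?** No. A patient who continues and has a valid Week 16 CPEX still lacks an accepted end-of-Period-1 procedure. Neither document says whether a test that was performed but rejected counts as completed. SAP 7.1 can be read as admitting anyone with a Week 16 test in the window, or only those who are already Completers. The patient would enter the MITT analysis in any case (SAP 4.1.2).

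**4. Power.** Inputs from Protocol 8.2 and SAP 11: two-sided one-sample t-test, alpha 0.05, SD 2.5, n = 30, mean change 2.0 (Period 2) and 1.2 (Period 1). Power comes from the noncentral t distribution with n − 1 degrees of freedom and noncentrality (mean/SD) × √n.

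- Plan's own figures: (2.0/2.5) × √30 = 4.38 gives 98.8%, consistent with the stated >95%. A change of 1.2 gives 71.9%, matching the stated 72%.
- Primary power with k of the 30 lost (k is assumed):

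| k lost | n | Power |
|---|---|---|
| 1 | 29 | 98.6% |
| 2 | 28 | 98.3% |
| 3 | 27 | 97.9% |
| 7 | 23 | 95.6% |
| 8 | 22 | 94.7% |

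Power stays above 95% until the eighth loss. These figures are for the t-test used for sample size; the SAP now plans an ANCOVA.

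**5. Selection.** The documents give no CPEX rejection or non-return rate. Assume that retained patients average 2.0 and that the k lost would have averaged m. The all-patient mean is [(30 − k) × 2.0 + k × m] / 30.

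- k = 1: m = 0 gives 58/30 = 1.93; m = 1.0 gives 59/30 = 1.97.
- k = 3: m = 0 gives 54/30 = 1.80; m = 1.0 gives 57/30 = 1.90.

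Completers show 2.0 throughout, so the excess is 0.03 to 0.20 mL/kg/min. The standard error at n = 30 is 2.5/√30 = 0.46. The planned loss from all causes is 33 − 30 = 3 patients.

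**The case against.** **The loss may not be due to the rule.** Continuing patients must attend at Weeks 10, 12, 14 and 16 for ECGs and drug levels. Many who will not return to repeat a Week 8 CPEX might miss Week 16 anyway. This stands. Section 4.6 costs data only in patients who would have attended later visits but did not repeat this one test, and nothing in the documents sizes that group. The Completer route is not weakened by this argument, because it excludes patients who did attend.

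**Week 8 matters in its own right.** Dose-response is a secondary objective, Period 1 against Period 2 is the first secondary endpoint, and a Period 1 snapshot is planned. This justifies asking for a valid Week 8 test. It does not justify making that test a condition of the primary analysis.

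**The effect is small.** Even 0.20 is under half a standard error, and it takes no response at all in the lost patients to reach it. This stands and limits the weight of the point.

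**Stronger readings that the documents do not support.** A reader might infer that a failed Week 8 test by itself removes the patient. It does not: the patient must also be unable or unwilling to return, and one who returns and fails again is not covered. A reader might also infer that this bullet flatly contradicts 6.4 and 6.8. Those conflicts are weak. After dosing, an invalid Baseline test is replaced by Screening with no repeat requested, and at end of treatment little dosing is left to stop.

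**Conclusion.** The point holds as one of avoidable selection. As written, 4.6 reaches an unrepeated, rejected Week 8 CPEX. Independently, the Completer definition probably excludes a patient without an accepted Week 8 test whatever 4.6 says, and SAP 7.1 does not settle it. Valid or obtainable Week 16 data may be dropped for a reason that the endpoint does not need.

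The likely size is modest: 0.03 to 0.20 mL/kg/min on a planned effect of 2.0. That range rests on two assumptions without support in the documents, namely 1 to 3 patients lost of 30 and a change of 0 to +1.0 in those patients. If they would have responded like the others, there is no bias. It would be wrong to read this as a power problem or as a demonstrated bias.

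**What to change.** 1. **Protocol.** Reconcile the second bullet of 4.6 with 6.4, 6.7, 6.8 and footnotes H and R, stating which visits it covers. Whether dosing continues after an unrepeated, invalid test is for the medical team.
2. **Analysis set.** In Protocol 8.3 and SAP 4.1.3, 5.3 and 7.1, define the primary analysis set as patients with a valid Baseline VO₂MAX (or the Screening substitute where the plan calls for one) and a valid Week 16 VO₂MAX within 7 days of Day 113. Treat an invalid or missing Week 8 CPEX as missing only for the Period 1 analysis and the Period 1 against Period 2 analysis. A sentence in SAP 5.3 alone would conflict with 8.3 and 4.1.3, so all four places must change together.

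**Cost.** One protocol clarification and a short SAP revision. The SAP introduction allows revisions before database lock, with reasons given in the study report. The primary analysis and the period contrast may then rest on slightly different patients, so report the number in each. The present Completer set can be kept as a sensitivity analysis.
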